11.6.2.9.7 Coagulation Indices

Prothrombin time (PT), international normalisation ratio (INR), and partial thromboplastin time (PTT) will be collected as specified in the individual modules. INR assessment should be repeated if any abnormalities above ULN in liver biochemistry occur, at 6-8 hours and 24 hours after occurrence of the abnormality. If INR is elevated at either timepoint, a subsequent INR assessment should be performed at 72 hours to ensure resolution.

Coagulation (PT/INR/PTT) will be collected for Part A and Part B at the times indicated below:

- Screening
- Pre-infusion on each dosing day
- EoT visit

11.6.2.9.8 Cardiac Troponin and BNP (or NTproBNP)

Blood samples for cardiac troponin and brain natriuretic peptide (BNP) or n-terminal pro b-type natriuretic peptide (NTproBNP) measurements will be collected for Part A and Part B (as specified in [Table 16](#) and [Table 17](#)) as follows:

- Screening
- As clinically indicated

Cardiac troponin I is preferred when available, however if not, cardiac troponin T is acceptable. To allow comparison with baseline, sites are requested to maintain consistency with the troponin assay used. Isolated troponin elevations are not sufficient to trigger dosing changes and should be evaluated in the context of other cardiac findings.

If an unscheduled ECG is performed for patient assessment, an electrolyte panel (ie, calcium, magnesium potassium) must be done. If clinically indicated, a troponin assay should coincide with this evaluation including referral to a cardiac specialist.

11.6.2.9.9 Cortisol, ACTH, and TSH

A blood sample for cortisol, adrenocorticotrophic hormone (ACTH) and thyroid-stimulating hormone (TSH) will be collected for Part A and Part B (as specified in [Table 16](#)) as follows:

- Screening (between Day -28 and -1)
- Cycle 1 Day 8; pre-infusion
- EoT visit

11.6.2.9.10 Serum Immunoglobulins

Samples for serum immunoglobulins will be collected for Part A and Part B (as specified in [Table 16](#)) as follows:

- Screening (between Day -28 and -1)
- Cycle 1 Day 8: pre-infusion
- EoT visit

11.6.2.9.11 Urinalysis

Urinalysis will be performed to assess glucose, protein, blood, ketones, and leucocyte esterase. Results must be available prior to dosing.

Samples for urinalysis will be collected for Part A and Part B at the times indicated below:

- Screening (-28 to -1)
- Pre-infusion on each dosing day
- EoT visit

11.6.2.9.12 Overnight Stays for TLS Monitoring

Overnight stays are recommended on infusion days during Cycle 1, but patients may be discharged prior to 24 hours post-dose, as per Investigator discretion, if their TLS laboratory values are appropriate, and if the patient is able to return for a follow-up clinic visit to complete required safety and laboratory assessments within the specified time windows. Thereafter, dosing as an inpatient will be as per Investigator discretion, based on prior tolerability and risk of TLS.

Tumour lysis syndrome monitoring should be performed (as specified in [Table 16](#)) at least twice in the first 24 hours after each administration of study treatment, and thereafter as clinically indicated.

11.6.2.9.13 Clinical and Laboratory Assessments for TLS

The classification of laboratory TLS and clinical TLS is described in [Appendix G](#). Patients will be evaluated for clinical signs and symptoms of TLS during treatment with AZD0466, and blood samples for laboratory assessments will be collected according to the respective module SoA.

Laboratory parameters from the clinical chemistry panel, which are indicative of TLS (according to the Howard modification of Cairo-Bishop criteria, [Appendix G](#)), including serum levels of uric acid, potassium, phosphate, calcium, and creatinine, will be evaluated. Blood urea nitrogen and lactate dehydrogenase may also be evaluated to aid assessment. Fluid

balance must be monitored per institutional standards. Blood samples for monitoring TLS will be collected at the timepoints as indicated in [Table 16](#) and as clinically indicated.

Recommended prophylaxis for TLS is outlined in [Appendix F](#).

11.6.2.10 Adverse Events and Serious Adverse Events

Refer to the core protocol (Section [8.3](#)).

11.6.2.10.1 Pregnancy

Refer to the core protocol (Section [8.3.13](#)).

11.6.2.10.2 Medication Error

Refer to the core protocol (Section [8.3.14](#)).

11.6.2.10.3 Overdose

Refer to the core protocol (Section [8.4](#)).

11.6.3 Human Biological Samples

11.6.3.1 Pharmacokinetics

Pharmacokinetic samples may be subjected to further analyses in order to further investigate the presence and/or identity of drug metabolites. These samples will be separate from the primary PK samples sent to the bioanalytical laboratory for analysis. Any results from such analyses will be reported separately from the CSR.

11.6.3.1.1 Urine Pharmacokinetics (in select cohort(s) only)

Samples for PK characterisation and potential analysis of urine metabolites will be collected in a select cohort(s) (based on emerging data) at the following times for Part A only. Note: Collection time begins from start of infusion:

Urine PK

Study period	Day	Timepoint
Cycle 1	Day 1	0-2 hours (+10 min)
		2-6 hours (± 15 min)
		6-10 hours (± 1 hour)
		10-24 hours (± 2 hours)
	Day 2	24-36 hours (± 2 hours)
	Day 4	0-2 hours (+10 min)
		2-6 hours (± 15 min)
		6-10 hours (± 1 hour)
		10-24 hours (± 2 hours)
	Day 5	24-36 hours (± 2 hours)
	Day 8	0-2 hours (+10 min)
		2-6 hours (± 15 min)
		6-10 hours (± 1 hour)
		10-24 hours (± 2 hours)
	Day 9	24-36 hours (± 2 hours)

11.6.3.1.2 Blood Sample for Plasma Pharmacokinetics

Blood samples should be taken from a different part of the body than where the study treatment is being infused, including if central line access is available, to prevent erroneous drug concentration readings. For example, if AZD0466 is being infused into the patient's right arm, then the blood sample should be collected from the left arm.

Blood samples for will be collected at the following times (collection time begins from start of infusion):

Blood Sample for Plasma Pharmacokinetics				
Study period	Day	Timepoint	Part A	Part B
Cycle 1	Day 1	Pre-infusion	X	X
		End of the infusion (+10 min) ^a		
	Day 4	Pre-infusion	X	X
		End of the infusion (+10 min) ^a		
	Day 8	Pre-infusion	X	X
		30 min after start of infusion (± 5 min)	X	X
		End of the infusion (+10 min) ^a	X	X
		2 hours from start of Day 8 infusion (± 15 min)	X	X
		6 hours from start of Day 8 infusion (± 30 min)	X	X
		9 hours from start of Day 8 infusion (± 1 hour) ^b	X	X
	Day 9	24 hours after the start of the Day 8 infusion (± 2 hours)	X	X
	Day 10	48 hours after the start of the Day 8 infusion (± 3 hours)	X	X
	Day 11	72 hours after the start of the Day 8 infusion (± 7 hours)	X	X
	Day 30/31	At MRD timepoint		X
Cycle 2	Day 1	Pre-infusion	X	X
		End of the infusion (+10 min) ^a	X	X
		2 hours from start of infusion (± 15 min)	X	X
		6 hours from start of infusion (± 30 min)	X	X
		9 hours from start of infusion (± 1 hour)	X	X
	Day 2	24 hours after the start of the Day 1 infusion (± 2 hours)	X	X
	Day 23-28	At MRD timepoint		X
Cycle 3 and beyond	Day 1	Pre-infusion	X	X
		End of the infusion (+10 min) ^a	X	X
	Day 23-28	At MRD timepoint		X

Note: Please refer to Section 11.6.2.6 for ECGs measured at all matched PK sample timepoints.

^a As close as possible to the end of the infusion, but permissible up to 10 minutes.

^b In the event that a planned collection is no longer possible at the scheduled timepoint, the Medical Monitor must be informed, and any collection outside allotted window must be discussed with the Medical Monitor.

11.6.3.1.3 CCI

[figure not shown]
11.6.3.2 Pharmacodynamics

11.6.3.2.1 CCI

Mandatory whole blood samples will be collected from all patients at the timepoints indicated in the SoA (Table 16 and Table 17) and as shown below. **CCI**

Note: Collection time begins with the start of infusion.

CCI

11.6.3.2.2 Pharmacodynamic CCI

Mandatory whole blood samples will be collected from all patients at the timepoints indicated in the SoA ([Table 16](#) and [Table 17](#)) and as shown below. CCI

Blood for Pharmacodynamic CCI

Study period	Day	Ramp-up (RU) or Target Dose (TD)	Timepoint	Part A	Part B
Screening	-	-	-	X	X
Cycle 1	Day 1	RU1 Day 1	Pre-infusion	X	X
			End of infusion (+10 min)	X	X
			6 hours after start of infusion (\pm 30 min)	X	X
	Day 2	RU1 Day 2	24 hours after start of Day 1 infusion (\pm 2 hours)	X	-
	Day 4	RU2 Day 1	Pre-infusion	X	X
			End of infusion (+10 min)	X	X
	Day 5	RU2 Day 2	24 hours after start of Day 4 infusion (\pm 2 hours)	X	-
	Day 8	TD Day 1	Pre-infusion	X	X
			End of infusion (+10 min)	X	X
			6 hours after start of infusion (\pm 30 min)	X	-
Cycle 2	Day 1	-	24 hours after start of Day 8 infusion (\pm 2 hours)	X	-
	Day 2	-	Pre-infusion	X	-
			6 hours after start of infusion (\pm 30 min)	X	-
Disease Progression/ End of treatment	-	-	24 hours after start of Day 1 infusion (\pm 2 hours)	X	-
			End of treatment	X	X

11.6.3.2.3 Peripheral Blood Smears

Mandatory peripheral blood smears will be collected at the timepoints indicated in the SoA (Table 16 and Table 17) and as shown below to evaluate CCI and normal blood cells and detect morphologic apoptotic responses in the blood. Blood smears will be obtained from CBC samples collected for Part A only. Note: Collection time begins with the start of infusion.

Peripheral Blood Smears - Part A Only			
Study period	Day	Ramp-up (RU) or Target Dose (TD)	Timepoint
Screening	-	-	-
Cycle 1	Day 1	RU1 Day 1	Pre-infusion
			End of infusion (+10 min)
	Day 2	RU1 Day 2	24 hours after start of Day 1 infusion (\pm 2 hours)
	Day 4	RU2 Day 1	Pre-infusion
			End of infusion (+10 min)
	Day 5	RU2 Day 2	24 hours after start of Day 4 infusion (\pm 2 hours)
	Day 8	TD Day 1	Pre-infusion
			End of infusion (+10 min)
			6 hours after start of infusion (\pm 30 min)
	Day 9	TD Day 2	24 hours after start of Day 8 infusion (\pm 2 hours)
Cycle 2	Day 1	-	Pre-infusion
	Day 2	-	24 hours after start of Day 1 infusion (\pm 2 hours)
Disease Progression/End of treatment	-	-	End of treatment

11.6.4 Human Biological Sample Biomarkers

11.6.4.1 Collection of Mandatory Samples for Biomarker Analysis

By consenting to participate in the study, the patient consents to the mandatory research components of the study.

Samples for biomarker research are required and will be collected from all patients in this study as specified in the SoA ([Table 16](#) and [Table 17](#)).

11.6.4.1.1 CCI

CCI

CCI

11.6.4.1.2 CCI

CCI

11.6.4.1.3 CCI

CCI

CCI

11.6.4.1.4 CCI

CCI

CCI

11.6.4.1.5 CCI

CCI

CCI

11.6.4.1.6 Bone Marrow Biopsy and Aspirate CCI

A mandatory pretreatment bone marrow biopsy and aspirate will be required for standard disease profiling and CCI (Section 11.6.1). Bone marrow biopsy samples will be collected in accordance with local/institutional guidelines and as per the process delineated in the laboratory manual CCI

Mandatory biomarker analysis will be also performed for any bone marrow aspirate and biopsy collected for disease assessment and at disease progression, according to the timepoints in Table 16 and Table 17. Note: The disease progression sample may be taken at the safety follow-up visit if not collected previously.

11.6.4.2 Collection of Optional Biomarker Samples

Refer to the core protocol (Section 8.6.1.1)

11.6.5 Other Study Related Biomarker Research

11.6.5.1 CCI

CCI

CCI

For storage, re-use, and destruction of biomarker samples see [Appendix C](#).

11.6.6 Optional Genomics Initiative Sample

Refer to the core protocol (Section [8.7](#)).

11.7 STATISTICAL CONSIDERATIONS - MODULE 1

11.7.1 Statistical Hypotheses

No formal statistical hypothesis testing is planned.

11.7.2 Sample Size Determination

11.7.2.1 AZD0466 Monotherapy Escalation - Part A

The primary objective of Part A is to identify the MTD and RP2D of AZD0466 monotherapy. In Part A, 3 to 12 DLT-evaluable patients may be treated in each dose level using an mTPI-2 design ([Guo et al 2017](#)) permitting approximately 36 DLT-evaluable patients for dose exploration. In addition, any tolerated dose level may be expanded at the discretion of the sponsor in discussion with the SRC to include up to a total of 18 patients for further evaluation of PK, PD, safety, or biological efficacy. Up to a total of 66 patients will be enrolled to yield approximately 36 DLT-evaluable patients and 18 patients for further exploration in Part A. This limits the number of patients exposed to AZD0466 consistent with the expected safety profiles of the study treatment, but includes sufficient patients to explore safety of the treatment, PK and effects on pharmacodynamic biomarkers, and to collect preliminary efficacy data.

11.7.2.2 Part B Monotherapy Dose Expansion

Separate expansion cohorts will enrol 4 distinct populations of patients with advanced haematological malignancies. Three of these expansion cohorts (Expansion Cohorts B1, B2, and B4) will recruit at least 21 patients, and one (Expansion Cohort B3) will recruit at least 25 patients. The total number of patients treated in Part B will be at least 88. These sample sizes have been determined to ensure confidence intervals constructed around the complete response rate (CR+CR_i), as calculated after all patients have had the opportunity to complete one treatment cycle, will provide sufficient information to enable decisions to be made around the likely success of future studies in these patient populations, using methodology described in [Frewer et al 2016](#).

Thresholds for decision making were set for each expansion cohort based on range of literature and expert opinion. For Expansion Cohort B1, a target value for response was set at 35%, with a lower reference value of 20%. If 7 or more responders are observed from 21 patients, there will be at least an 80% chance that the true response rate is at least 20%, which may promote a positive decision. If 4 or fewer responders are observed, then there is a 10% or less chance that the true rate is at least 35%, which may lead to a futility decision. If

the true rate of response is 15%, then, with 21 patients, there is an 80.3% probability of a result that may trigger a decision to stop further development in this population due to futility. This analysis will be performed using the ITT population.

An IA as described in Section 11.7.9 will be performed in each expansion cohort when 12 patients have had the opportunity for one cycle of treatment and is response evaluable as per [Table 21](#). The number of patients is based on the operating characteristics of the cohort-specific decisions using the approach as described in [Frewer et al 2016](#).

In Expansion Cohort B1, if 5 or more responders are observed from 12 patients, then there is at least an 80% chance that the true response rate is at least 20%, which may promote a decision to continue to full recruitment. It may be considered futile to continue development of this cohort if there is < 10% probability for the response rate to be greater than 35%. This translates to observing one or zero responders out of 12 patients.

For the other expansion cohorts, Expansion Cohorts B2, B3, and B4, the target values and lower values for response were set at (40%, 25%), (25%, 13%) and (40%, 25%) respectively. Descriptive statements for these expansion cohorts are given below, with values for the final (and interim) analyses presented using brackets for the IA.

For Expansions Cohorts B2 and B4, a target value for response was set at 40%, with a lower reference value of 25%. In either of these cohorts, if 8 (5) or more responders are observed from 21 (12) patients, there will be at least an 80% chance that the true response rate is at least 25%, which may promote a positive decision. If 5 (1) or fewer responders are observed, then there is a 10% or less chance that the true rate is at least 40%, which may lead to a futility decision. If the true rate of response is 20%, then with 21 (12) patients, there is a 76.9% (55.8%) probability of a result that may trigger a decision to stop further development in these populations for futility.

For Expansion Cohort B3, a target value for response was set at 25%, with a lower reference value of 13%. If 6 (3) or more responders are observed from 25 patients there will be at least an 80% chance that the true response rate is at least 13%, which may promote a positive decision. If 3 (0) or fewer responders are observed, then there is a 10% or less chance that the true rate is at least 25%, which may lead to a futility decision. If the true rate of response is 8%, then with 25 (12) patients, there is an 86.5% (36.7%) probability of a result that may trigger a decision to stop further development in these populations due to futility.

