11.7.9 Interim Analyses

Each cohort in Part B will have an internal IA for futility, with the potential to stop or trigger a combination expansion (to be added via a protocol amendment), followed by a sponsor decision towards further development if the cohort proceeds to full recruitment. During the IA, enrolment may be paused in order to fully evaluate the results. Data for the IA will include all data collected up to the point when the twelfth patient within the cohort has had the opportunity to complete one cycle of treatment with AZD0466 and is response evaluable as per [Table 21](#). The Evaluable for Response population will be used for this analysis. Contingent on the outcome of the IA, recruitment will then continue to full recruitment.

The interim analyses for efficacy will consist of summaries rates of best response (CR+CR_i) with one-sided lower 80% and upper 90% exact confidence limits compared to the cohort-specific target response rates as described in Section 11.7.2.

An IA for safety in Part B will take place at the same time as the analysis for efficacy, based on the Safety population. Rates of AEs leading to study treatment discontinuation will be compared to pre-specified criteria to inform a ‘stop’ or ‘consider’ decision. The unacceptable rate of AEs leading to study treatment discontinuation is set at 30%. For example, in 12 patients, one or fewer of these AEs would provide at least an 80% chance that the true rate is not greater than 30%. If 4 or more events are observed in 12 patients at the interim then there will be a lower than 10% chance that the rate is under 15% and the study may be stopped due to safety. If the IA takes place with a number other than 12 patients then the threshold rates of AEs leading to discontinuation may differ from the example provided.

The SAP will describe the planned interim analyses in greater detail.

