	
• Sections 8.10.2.2, 8.10.2.3, 8.10.3.1 Efficacy evaluation
• Disease progression revised as treatment failure and relapse, as applicable.• Section 8.10.3.3 Minimal/Measurable Residual Disease (Part B Only) removed• Section 8.10.3.4 added for haematological response in intermediate and higher risk MDS patients (Part A Only)• Section 8.13.1.2 Part B Monotherapy Dose Expansion removed• Section 8.14 Interim Analysis changed to (Not applicable)• Minor editorial changes

1 INTRODUCTION - Core

This is a modular, Phase I/II study of AZD0466 as monotherapy or in combination with other treatments in patients with advanced haematological malignancies. The core sections of the SAP contains information applicable to all analyses planned in this study, more specific details are provided in the sections related to the individual modules.

The sponsor made the decision to terminate the study on July 28, 2023. Recruitment was stopped on June 16, 2023 and patients were followed up until the planned LPLV date of August 8, 2023. At the time of stopping recruitment, Module 1 Part A, and Module 2 were ongoing. The decision was also made not to initiate Module 1 Part B. Therefore, this statistical analysis plan (SAP) provides the technical elaboration of the statistical analyses for Module 1 Part A, and Module 2.

The analyses described for Module 1 and 2 in this SAP are based upon the following study documents and reporting standards:

- Study Protocol, Version 4.0 (September 29, 2022)
- Electronic Case Report Form (eCRF), Version 8.0 (March 13, 2023)
- AZ Corporate CSRHLD Reporting Standards v3.3
- Oncology Guidance Version 3.0
- Early Phase Oncology Guidance Version 1.0
- AZ Guideline: Pharmacokinetic Evaluations in Clinical Studies v2.3

Specifications for tables, figures, and listings are contained in a separate document.

2 STUDY OBJECTIVES – Core

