8.14 Interim Analyses (Not applicable)

9 INTRODUCTION – Module 2

Module 2 will be initiated by the SRC (Appendix A5 of the study protocol) after a tolerated dose of AZD0466 has been determined in Module 1. This is a DDI study that will evaluate AZD0466 with voriconazole, a strong inhibitor of CYP3A4.

For further general study information refer to Section 1.

10 STUDY OBJECTIVES - Module 2

The core objectives and endpoints for the study are listed in Sections 2.1, 2.2 and 2.3; additional secondary endpoints for Module 2 are listed in Section 10.1

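### Cohorts B2 and B4: the printed interim futility cut-off (1 of 12) does not give the stated 55.8% futility probability; it gives 27.5%, and 55.8% belongs to a cut-off of 2 of 12.

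*Protocol*

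**What the plan says.** Section 11.7.2.2 of the protocol sets out, for each Part B expansion cohort, response counts that would support continuing or stopping. For B2, B3 and B4 the final value is printed first and the interim value follows in brackets.

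For B2 and B4 the target response rate is 40% and the lower reference value is 25%. A positive signal arises "if 8 (5) or more responders are observed from 21 (12) patients". The futility statement is "If 5 (1) or fewer responders are observed, then there is a 10% or less chance that the true rate is at least 40" per cent, "which may lead to a futility decision". For a true rate of 20%, the protocol then says "there is a 76.9% (55.8%) probability of a result that may trigger a decision to stop".

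Two other places bear on the rule. For Cohort B1 (target 35%), the same section derives the interim count directly from the 10% criterion: "This translates to observing one or zero responders out of 12 patients". Section 11.7.9 describes the interim efficacy analysis as "one-sided lower 80% and upper 90% exact confidence limits compared to the cohort-specific target response rates".

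The SAP (version 2.0, section 1) records that "The decision was also made not to initiate Module 1 Part B". Its section 8.14 marks interim analyses as not applicable, so it holds no figures on this point.

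**The concern.** The futility probability at a given true rate is fixed by the cut-off and the sample size. Once 12 patients, a cut-off of 1 and a true rate of 20% are stated, the probability follows, and it is about half the printed figure. Either the threshold or its stated operating characteristic is therefore wrong.

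If the cut-off is wrong, a cohort with 2 responders of 12 would draw no futility signal from the printed count, although the 10% criterion calls for one. If the probability is wrong, the interim look is described as about twice as likely to flag a poor cohort as it really is. Section 11.7.2.2 justifies the 12-patient interim size by the operating characteristics of these decisions, so the figure is part of the design rationale.

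**Working it through.** **Inputs (protocol 11.7.2.2).** B2/B4 interim: n = 12, printed futility cut-off k = 1, target 40%, assumed poor true rate 20%, stated futility probability 55.8%. B2/B4 final: n = 21, k = 5, stated 76.9%.

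**Formula.** P(X ≤ k | n, p) = Σ over x = 0 to k of C(n, x) pˣ (1 − p)ⁿ⁻ˣ.

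**Step 1: reproduce the other stated probabilities.**
- B1 final: P(X ≤ 4 | 21, 0.15) = 80.25% (printed 80.3%)
- B2/B4 final: P(X ≤ 5 | 21, 0.20) = 76.93% (printed 76.9%)
- B3 final: P(X ≤ 3 | 25, 0.08) = 86.49% (printed 86.5%)
- B3 interim: P(X = 0 | 12, 0.08) = 0.92¹² = 36.77% (printed 36.7%, apparently truncated)

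All four agree, so this is the method the protocol used.

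**Step 2: the B2/B4 interim at a true 20%.**
- P(X = 0) = 0.8¹² = 0.0687
- P(X = 1) = 12 × 0.2 × 0.8¹¹ = 0.2062
- P(X = 2) = 66 × 0.2² × 0.8¹⁰ = 0.2835
- P(X ≤ 1) = 0.2749, or 27.5%
- P(X ≤ 2) = 0.5583, or 55.8%

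The printed probability matches a cut-off of 2. The gap is the probability of exactly 2 responders, 28.3%, far beyond rounding. Keeping a cut-off of 1 with n = 12, 55.8% would need a true rate of about 12.2%. Keeping 20%, it would need 7 patients (57.7%) or 8 (50.3%), not 12.

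**Step 3: what the 10% criterion gives.** At the 40% target with n = 12: P(X ≤ 1) = 2.0%, P(X ≤ 2) = 8.3%, P(X ≤ 3) = 22.5%. The largest qualifying count is 2. The exact (Clopper–Pearson) one-sided upper 90% limit is 38.6% for 2/12, below 40%, and 47.5% for 3/12, above it. Reading the criterion as a posterior probability does not change this: 2/12 gives 5.8% with a uniform prior and 4.3% with a Jeffreys prior, and 3/12 gives 16.9% and 14.4%.

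**Step 4: compare all the printed cut-offs.**

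| Cohort and look | Target | Printed cut-off | P(X ≤ cut-off) at target | Same, one count higher |
|---|---|---|---|---|
| B1 final | 35% | 4/21 | 9.2% | 20.1% |
| B1 interim | 35% | 1/12 | 4.2% | 15.1% |
| B2/B4 final | 40% | 5/21 | 9.6% | 20.0% |
| **B2/B4 interim** | **40%** | **1/12** | **2.0%** | **8.3%** |
| B3 final | 25% | 3/25 | 9.6% | 21.4% |
| B3 interim | 25% | 0/12 | 3.2% | 15.8% |

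Every other cut-off is the largest count that meets 10%. Only the B2/B4 interim leaves room for one more responder.

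**Step 5: consequence over both looks.** Assume the signal is acted on, enrolment stops at 12 when it fires, the same patients count at both looks, and the final cut-off is 5/21. With interim cut-off c:
- Overall futility = P(X₁₂ ≤ c) + Σ over x = c + 1 to 5 of P(X₁₂ = x) · P(X₉ ≤ 5 − x)
- Expected enrolment = 12 + 9 · P(X₁₂ > c)

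| | Cut-off 1 | Cut-off 2 |
|---|---|---|
| True 20%: interim futility | 27.5% | 55.8% |
| True 20%: futility over both looks | 77.4% | 79.8% |
| True 20%: expected enrolment per cohort | 18.5 | 16.0 |
| True 40%: interim futility | 2.0% | 8.3% |
| True 40%: futility over both looks | 10.1% | 13.4% |

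**The case against.** The case against concerns weight rather than the arithmetic.

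- **The cut-off sentence is true on its own.** At 1 of 12 the tail probability is 2.0%, which is within 10%. That stands, but it does not rescue the 55.8% that follows.
- **No rule says the cut-off must be the largest qualifying count.** That is inferred from the other five. A deliberately stricter interim cut-off would be legitimate, in which case only the percentage is wrong. This also stands, and is why both repairs are offered.
- **The printed count is not the only statement of the interim rule.** Section 11.7.9 compares exact limits with the target, so an analyst following it would see a futility signal at 2/12 whatever digit section 11.7.2.2 prints. This limits the practical harm, but it also means the two sections disagree at 2/12.
- **Part B never opened, and the rule is non-binding.** Both are correct. No patient met this threshold and no output depends on it.
- **The two-look figures go beyond the protocol.** They treat a non-binding signal as binding and assume one population, whereas the interim uses the Evaluable for Response set and the later analysis uses the ITT set. They are approximate and show only the order of the effect.

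An undefined zone between the futility and positive counts is a feature of every cohort's rule and is not part of this point.

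**Conclusion.** The inconsistency is real. For B2 and B4, an interim cut-off of 1 of 12 carries a 27.5% futility probability at a true rate of 20%, not the stated 55.8%. Both the stated probability and the 10% criterion point to a cut-off of 2, but the documents do not establish which figure is the slip.

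The central result needs only the printed sample size, cut-off and true rate, with independent binomial responses. Under the two-look assumptions above, total futility at a true 20% moves by only 2.4 points (79.8 − 77.4), while expected enrolment differs by about 2.5 patients per cohort (18.5 − 16.0). The effect is therefore mainly on how early a poor cohort is flagged. The error should be corrected as a matter of the stated design. It has no bearing on the reported results, because Part B was not initiated.

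**What to change.** Reconcile the two figures in section 11.7.2.2, in one of two ways:

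- Change the bracketed interim futility count for B2 and B4 from 1 to 2. This agrees with the stated 55.8%, with the 10% criterion (8.3%) and with the exact-limit comparison in section 11.7.9 (38.6% against 40%).
- If 1 was intended, replace 55.8% with 27.5% and state that the interim futility rule for these cohorts is deliberately stricter than 10%.

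The sponsor should confirm which was meant from the original design calculations. The cost is one digit, or one percentage and a sentence, in the protocol. No SAP output changes. Any future protocol that reuses the Part B text should carry the corrected version.
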